1.1 Background

Primary immune thrombocytopenia (ITP) is an acquired, immune-mediated disorder of adults and children. It is defined as a platelet count of less than $100 \times 10^9/L$, in the absence of other causes or disorders that may be associated with thrombocytopenia.

Incidence estimates for adult-onset ITP are reported to range from 1.6 to 3.9 per 100,000 per year. The incidence of ITP follows a multimodal distribution pattern, with peaks in young children, young adults and the elderly, with the highest age-specific incidence in individuals over 60 years (Terrell 2010). The overall prevalence of ITP in adults has been estimated to be 9.5 per 100,000, ranging from 4.1 per 100,000 in younger ages (19 to 24 years) to 16 per 100,000 in older age groups (55 to 64 years). Immune thrombocytopenia is found worldwide and has similar epidemiologic patterns across regions (Arnold 2013).

Most commonly, ITP patients have asymptomatic thrombocytopenia, however patients usually present at hospital and seek medical help once bleeding symptoms occur. Although some patients bleed with platelet counts $< 30 \times 10^9/L$, many do not. Bleeding symptoms characteristic of ITP (“platelet-type bleeding”) include skin bleeding (i.e., bruises, non-palpable purpura, or petechiae), oral hemorrhagic blood blisters (purpura) or oral petechiae, epistaxis, menorrhagia, or gastrointestinal bleeding. The most feared life-threatening complication is intracerebral hemorrhage, reported in 1.5 to 1.8% of adult patients (Lambert 2017, Hoffman 2013).

The degree of bleeding is largely dependent on the severity of thrombocytopenia, with platelet counts < 20 to $30 \times 10^9/L$ conferring the greatest risk of clinically significant bleeding (George 1996; Guidelines 1 British Society for Haematology 2003). Mild hemorrhages presenting with bruising and petechiae are most common, but severe hemorrhages involving the gastrointestinal and genitourinary tract are well known complications of the disease, and occur in $\sim 10\%$ of adult ITP patients. The frequency of death from hemorrhage in patients with platelet counts $< 30 \times 10^9/L$ is estimated to be between 1.6 and 3.9% per patient year, although the frequency is influenced by age, severity and duration of thrombocytopenia (Cohen 2000).

Based on the disease duration from initial confirmed ITP diagnosis, there are 3 categories of patients: newly diagnosed (between time of diagnosis and 3 months), persistent ITP (between 3 and 12 months from diagnosis), and chronic ITP (cITP) (reserved for patients with ITP lasting for more than 12 months). This clinical categorization inversely correlates with patients’ chance of achieving spontaneous remission of the disease (i.e., the longer the duration of disease, the lower the chance for spontaneous remission) (Rodegiero 2009, Hoffman 2013, Provan 2010).

Chronic ITP has been associated with a risk of death that is up to four times higher than that of the general population. ITP patients are more likely to die of bleeding, infection, and hematologic malignancies. Some deaths are attributable to adverse events (AEs) of treatment rather than the disease. Quality of Life (QoL) in patients with ITP is lower than that of the general population, which is at least partially a result of high prevalence of fatigue that appears to be independent of platelet count levels (Portielje 2001, Hoffman 2013, Stasi 2004, Profit 2006, George 2006)

The goal of therapy in ITP is not to normalize the platelet count but to achieve a platelet count that confers adequate hemostasis and minimizes the risk of clinically significant bleeding for the individual patient, avoiding treatment-related toxicity. Therefore, the choice and the management of each treatment must be conducted for each patient on a case-by-case basis. In general, treatment is seldom required when platelets are > 20 to $30 \times 10^9/L$. For patients with platelets $< 20 \times 10^9/L$, treatment is required, but depends on a full assessment of the patient lifestyle, occupation, bleeding history, comorbidities, and other factors (Provan 2010, Rodeghiero 2009).

Observational data from ITP patient cohorts indicate that risk of clinically significant bleeding increases with increasing severity of thrombocytopenia and as such, a platelet threshold of < 20 to $30 \times 10^9/L$ is typically a trigger for treatment, irrespective of bleeding manifestations. Treatment guidelines established by the American Society of Hematology (ASH) and the International Working Group (IWG) consensus panel of expert clinicians also indicate that it is appropriate to initiate treatment for newly diagnosed ITP patients with platelet counts of $< 30 \times 10^9/L$ (Neunert 2011, Provan 2010).

Current therapies

First-line treatment has remained unchanged for decades and comprises corticosteroids in 60 to 70% of patients, intravenous immunoglobulin (IVIG) in approximately 20%, and anti-D immune globulin (less than 10% in countries where anti-D is available). Corticosteroids are inexpensive and raise platelet counts rapidly within 2 to 14 days in approximately 75% of patients. Corticosteroids will generally induce a response within the first 2 weeks, but less than 25 to 30% of patients will sustain responses and will relapse within the first year, most commonly during steroid taper or shortly after discontinuation (Table 1-1) (Cooper 2017, Wong 2017).

Side effects of steroids are common and predictable, and have a significant impact on patients' QoL. The most common steroid-related AEs include weakness, impaired cognition and insomnia, mood changes, weight gain, headache, impaired glucose metabolism, as well as increased risk of infections due to immunosuppressive effects, and osteoporosis due to the effect on bone marrow density. Currently available corticosteroids for ITP include prednisone, prednisolone, methylprednisolone and dexamethasone, with prednisone and dexamethasone being the most widely used.

Prednisone, rather than dexamethasone, has been used predominantly as first-line treatment, but the rate of sustained response with prednisone and dexamethasone seem overall similar. The typical dosing regimen for prednisone is 0.5 to 2 mg/kg bodyweight daily for four weeks until the maximum dose is achieved, followed by tapering. Approximately two-thirds of patients demonstrate an initial response to prednisone, but only a limited fraction of patients experience long-term remission. However, despite this, prednisone remains the first-line corticosteroid of choice. There are conflicting results, and no clear consensus on whether use of high dose dexamethasone (HD-DEX) vs prednisone is preferable, even though there is increasing evidence, including data from randomized prospective clinical trials demonstrating that HD-DEX provides a more effective and rapid response as the initial treatment regimen for ITP in comparison to conventional prednisone (Mithoowani 2016, Mashhadi 2012, Wei 2016, Nakazaki 2012, Sakamoto 2014).

Table 1-1 First-line treatment options for patients with ITP

Treatment	Typical dose/regimen	Efficacy	Safety
Prednisone	0.5–2 mg/kg/day, for 2–4 weeks until a response is seen, followed by tapering over several weeks	Initial response: 60–80% Sustained response: 20–47%	AEs vary with the dose and duration, but include weight gain, anxiety, insomnia, and diabetes
Dexamethasone	40 mg/day, for 4 days every 2–4 weeks, for 1–4 cycles	Initial response: up to 90% Sustained response: 40–50% Repeated cycles may result in response rates up to 80%	Weakness, insomnia, and impaired cognition
IVIG	0.4 g/kg/d for 5 days or 1 g/kg/d for 1–2 days	Initial response: up to 80% Platelet count usually returns to pretreatment levels within 2–4 weeks, persists for months in few patients	Common: headache, hypertension, and chills Rare: hemolysis and neutropenia
Anti-D	50–75 µg/kg	Similar to IVIG, dependent on dose	Common: hemolysis Rare: intravascular hemolysis, can be fatal

Source: [Provan 2010](#)

In general, 60-70% of adults with acute ITP achieve an initial response; even higher response rates are reported in children. Rates of sustained response with corticosteroid treatment (usually defined as a platelet count ≥ 50 or $\geq 100 \times 10^9/L$ at 6-12 months, with different timeline and platelet count thresholds within different publications) are generally low and vary from 20% to 47%. With longer follow-up, the risk of relapse increases in adults who experience an initial response.

Many of the currently available treatments, in particular, high doses of steroids, are associated with significant morbidity. Historical data has shown that mortality from ITP more often results from infectious complications of steroid treatment and splenectomy rather than directly from bleeding. Thus, there is an important need for a tolerable therapy for patients that do not experience early ITP remission with steroid treatment.

Options for salvage therapy include retreatment with corticosteroids, switching from one steroid type to another, a combination of first-line agent(s), or treatment with a second-line agent. According to current guidelines available modalities for second line treatment options for ITP patients have quite different mechanisms of action. They are broadly classified into those that are given only once (or for only one course) and are intended to induce long-term remission (splenectomy, rituximab) and those that need continued or chronic administration (corticosteroids, immunosuppressive agents and Thrombopoietin Receptor Agonists [TPO-RAs]).

There are limited data about duration of steroid recycling, but such regimens vary from a few months up to a few years of repeated steroids use and/or switching from one steroid type to another. The incidence of steroid-derived AEs, in general, depends greatly on both the average dose and cumulative duration of use, indicating that it is essential to both complete whole courses of therapy in as short a period as possible and to reduce the total amount of administered corticosteroids.

While corticosteroids remain the standard of care for ITP, high relapse rates and considerable toxicity associated with long-term corticosteroid use highlight a significant unmet medical need in the management of ITP particularly for those patients who relapse after initial treatment. Novel therapeutic approaches are warranted that achieve a sustained response and reduce the need for long-term corticosteroid use.

1.2 Purpose

[figure not shown]
The purpose of this trial is to assess the ability of eltrombopag to induce sustained treatment-free remission in ITP patients who failed to respond or have relapsed after an initial treatment with steroids.

This is supported by medical experts' experience and limited published evidence indicating that a certain proportion of patients are able to achieve a stable response and sustained remission during treatment with TPO-RA earlier in the course of the disease and are able to discontinue treatment ([Bussel 2015](#), [Gonzalez-Lopez 2015](#), [Newland 2016](#)). TPO-RA used earlier than 12 months from disease diagnosis might reduce toxicity from steroid exposure and can provide a sustained remission. However, an analysis of data collected prospectively and powered to assess whether TPO-RA can behave in this manner is lacking.

There is insufficient evidence to create a treatment sequence recommendation for patients who relapsed or who failed to respond after first-line steroid treatment within 3-12 months from initial diagnosis. The most appropriate treatment sequence for those ITP patients should eliminate an unacceptable level of uncertainty and currently is not addressed in any of the guidelines.

We will therefore conduct a prospective trial of eltrombopag in patients with ITP, who are refractory to or who relapsed after initial treatment with first-line steroids, to assess the ability of eltrombopag to induce treatment-free sustained remission.

This trial will help by closing a gap that exists in the medical community, which is to generate prospective data within clinical trial setting that will demonstrate that eltrombopag could be the treatment option considered after first-line steroid treatment. The definition of 'first round of steroids' is not standardized, with different duration of steroids cycles being considered as "first round" ([Provan 2011](#), [Neunert 2011](#), [Gutierrez-Espindola 2003](#)).

2 Objectives and endpoints

Table 2-1 Objectives and endpoints

Objective(s)	Endpoint(s)
Primary Objective(s)	Endpoints for primary objective(s)
1. To assess ability of eltrombopag to induce sustained remission by month 12 in ITP patients who relapsed or failed to respond to first-line steroid treatment.	1. Proportion of patients with sustained remission (R) by month 12 where sustained remission is defined as: 
reach platelet count $\geq 100 \times 10^9/L$ (complete response [CR]) and then maintain platelet counts around $100 \times 10^9/L$ for 2 months (no counts below $70 \times 10^9/L$) AND thentaper off the drug until treatment discontinuation (see Section 9.1) while,maintain platelet count $\geq 30 \times 10^9/L$ in the absence of bleeding (no bleeding AEs) or use of any rescue therapy (see Section 6.2.3) until month 12.
Secondary Objective(s)	Endpoints for secondary objective(s)
1. To assess the duration of sustained remission after treatment discontinuation by month 12 and by month 24	1a. Median duration of sustained remission (weeks) counted from last dose of eltrombopag to month 12 for patients with sustained remission (R) 1b. Estimated median duration of sustained remission (weeks) by month 24 for patients who are in sustained remission (R) at month 12 and enter 12 months follow-up period using Kaplan-Meier method 1c. Estimated median duration of sustained remission (weeks) by month 24 for all patients using Kaplan-Meier method.
2. To assess the proportion of patients maintaining a sustained remission after treatment discontinuation until month 24.	2. Proportion of sustained remission (R) patients at months 15, 18, 21, and 24.
3. To assess the ability of eltrombopag to induce early response by month 1	3. Number (%) of patients with platelet count $\geq 50 \times 10^9/L$ at least once by month 1 (first month) without bleeding and no rescue therapy
4. To assess the ability of eltrombopag to induce a recovery response, in case of loss of response during or after tapering of eltrombopag until month 24	4. Number (%) of patients with at least one platelet count $\geq 30 \times 10^9/L$ after eltrombopag is re-introduced, in case of loss of response ($< 30 \times 10^9/L$ and/or bleeding event) without bleeding and no rescue therapy by month 12 and 24
5. To assess the platelet count from baseline and every 3 months until month 24	5. Absolute and relative change in platelet count from baseline to 3, 6, 9, 12, 15, 18, 21, and 24 months and end of treatment
6. To assess the ability of eltrombopag to maintain platelet count $\geq 30 \times 10^9/L$ within 12 months and every 3 months until month 24	6. Number (%) of patients who maintain a platelet count $\geq 30 \times 10^9/L$ from the first time of reaching that level to month 3, 6, 9, 12, 15, 18, 21, 24, and end of treatment without bleeding and no rescue therapy

Objective(s)	Endpoint(s)
7. To evaluate patient-Health Related outcome measures for health-related quality of life (fatigue level of the patients through FACIT) & FACT-Th6 and SF-36v2 questionnaires from baseline and every 3 months to month 24 and end of treatment	7. The analysis of HRQoL parameters; fatigue level of the patients through FACIT & FACT-Th6, SF-36v2 questionnaires. Change in scores from baseline to month 3, 6, 9, 12, 15, 18, 21, 24, and end of treatment
8. To explore the overall impact of side effects on treatment via the GP5 at baseline, month 12, and end of treatment	8. Overall change from baseline to month 12 and end of treatment will be assessed
9. To explore treatment satisfaction with TSQM-9 at baseline, month 12, and end of treatment	9. Overall change from baseline to month 12 and end of treatment will be assessed
10. To evaluate the safety and tolerability of eltrombopag	10. Number (%) and severity of patients with AEs, serious AEs (SAEs), AEs leading to discontinuation, AEs leading to dose adjustments, AEs of special interest. Change from baseline in vital signs and clinical laboratory tests

[figure not shown]
FACIT=Functional Assessment of Chronic Illness Therapy; FACT=Functional Assessment of Cancer Therapy; FACT-Th6=Functional Assessment of Cancer Therapy – Thrombocytopenia 6-item version; GP5-bothered by symptoms component of the FACT-G assessment; HRQoL=Health Related Quality of Life; SF-36=Short Form-36; [REDACTED]

TSQM-9=Treatment Satisfaction Questionnaire for Medication; [REDACTED]

3 Study design

This is a phase II, open-label, prospective, single-arm, study to assess ability of eltrombopag to induce sustained remission in adult patients with ITP who are refractory or relapsed after first line steroids. The study design is provided in [Figure 3-1](#).

Figure 3-1 CETB115J2411 study design

*Sustained remission is defined as patients who:

Reach platelet count $\geq 100 \times 10^9/L$ (complete response [CR]) and then maintain platelet counts around $100 \times 10^9/L$ for 2 months (with no counts below $70 \times 10^9/L$) AND then taper off the drug until treatment discontinuation while, maintaining platelet count $\geq 30 \times 10^9/L$ in the absence of bleeding (no bleeding AEs) or use of any rescue medication until month 12

Population:

- Patients with ITP, ≥ 18 years of age
- Relapsed or failed to respond after first line steroid treatment
- Platelet count $< 30 \times 10^9/L$ and need for treatment

Patients with confirmed diagnosis of ITP, who have failed to respond or who have relapsed following initial response after a first-line of steroid therapy with or without intravenous immunoglobulin (IVIG) (if used as a rescue therapy) will be screened, and if eligible, will receive eltrombopag. First line of steroid therapy will be defined as: prednisone/prednisolone 0.5 to 1mg/kg/day for a minimum of 2 weeks, or minimum of 1 course of high-dose dexamethasone 20 to 40 mg/day for consecutive 4 days \pm IVIG (used as rescue therapy). Maximum exposure to high-dose steroids treatment (steroids tapering time excluded) should be limited to: 4 weeks of high dose prednisone/prednisolone or 3 courses of high-dose dexamethasone. Overall exposure to steroids must not be longer than 3 months, including period of dose tapering.

In this study, the starting dose will be 50 mg eltrombopag QD (starting dose for Asian patients will be 25 mg QD, reduced as per [Section 6.1](#)).

This eltrombopag starting dose is consistent with the dosing guidelines that have been approved for eltrombopag use in adult patients with chronic ITP.

Taper-off and treatment discontinuation: Patients who reach CR (platelet count $\geq 100 \times 10^9/L$) and maintain counts around $100 \times 10^9/L$ for 2 months (no platelet count below $70 \times 10^9/L$) will be eligible for taper-off and treatment discontinuation. Duration of tapering will vary depending on the starting dose and the response of the patient: decreases in eltrombopag

[figure not shown]
dose will be performed by a 25 mg reduction every 2 weeks up to 25 mg on alternate days for 2 weeks until treatment discontinuation.

Patients who successfully taper off, i.e. discontinue eltrombopag and maintain platelet count $\geq 30 \times 10^9/L$ in the absence of bleeding or use of any rescue therapy will be followed up through the duration of the trial (to month 12). In case of relapse, patients will be offered a new course of eltrombopag treatment within this timeframe, starting at a dose of 50 mg.

Patients with bleeding, or perceived risk of serious bleeding, will be allowed to receive rescue therapy as per physician decision, irrespective of platelet counts.

A schematic depicting an example of a patient with sustained remission is provided in [Figure 3-2](#). Individual patient study experience will vary dependent on time to response and duration of eltrombopag tapering.

Figure 3-2 Example of a patient with sustained remission by Month 12

4 Rationale

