Data analysis	
Continuous variables will be summarized by number of patients, mean, standard deviation, minimum, median, and maximum. For selected parameters, 25th and 75th percentiles will also be presented.
 
Categorical variables will be summarized by frequencies and percentages. The 95% confidence interval (CI) using the Clopper-Pearson method will be provided for selected parameters.
 
Kaplan-Meier method will be used for time to event analyses.
 
The primary endpoint is the proportion of patients with sustained remission by month 12, where sustained remission (R) is defined as:
 
• reach platelet count $\geq 100 \times 10^9 / \text{L}$ (CR) and then maintain platelet counts around $100 \times 10^9 / \text{L}$ for 2 months (no platelet count below $70 \times 10^9 / \text{L}$) AND then• taper off the drug until treatment discontinuation while,• maintain platelet count $\geq 30 \times 10^9 / \text{L}$ in the absence of bleeding (no bleeding AE) or use of any rescue therapy until month 12. 
The number (%) of patients with sustained remission (R) by month 12 will be summarized together with 95% CI using the Clopper-Pearson method. A binomial test for one proportion, H0: P=0.15 vs. H1:P>0.15 will be performed to test if the proportion of patients with sustained remission is greater than 15%.

Key words	Eltrombopag, immune thrombocytopenia, ITP, corticosteroids

1 Introduction

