12.5.1 Efficacy endpoint(s)

1. To assess the **duration of sustained remission** after treatment discontinuation

1a) Summary statistics for the duration of sustained remission (weeks) counted from last dose of eltrombopag to month 12 for patients with sustained remission (R) will be provided.

1b) Kaplan-Maier analyses for the duration of sustained remission (weeks) counted from last dose of eltrombopag to relapse for patients with sustained remission (R) at month 12 and who enter 12 months follow-up period. The patients who do not relapse/die by month 24 will be censored.

1c) Kaplan-Maier analyses for the duration of sustained remission (weeks) counted from last dose of eltrombopag to relapse for all patients. The patients who do not relapse/die by month 24 will be right-censored. The duration will be considered as 0 for patients who do not manage to taper off eltrombopag per protocol i.e. do not reach sustained remission.

2. To assess the proportion if patients maintaining a sustained remission after treatment discontinuation until month 24.

Number (%) of patients who are in sustained remission at months 15, 18, 21, and 24 will be provided.

3. To assess the ability of eltrombopag to induce **early response by month 1**

Number (%) of patients who reach platelet count $\geq 50 \times 10^9/L$ at least once within the first month (month 1) without bleeding events and no rescue therapy will be provided.

4. To assess the ability of eltrombopag to induce a **recovery response**, in case of loss of response during or after tapering of eltrombopag

Number (%) of patients with at least one platelet count $\geq 30 \times 10^9/L$ after eltrombopag is re-introduced, in case of loss of response ($< 30 \times 10^9/L$ and/or bleeding event) without bleeding events and no rescue therapy will be provided.

5. To assess the **platelet count** from baseline to 3, 6, 9, 12, 15, 18, 21, 24 months

Absolute and relative change in platelet count from baseline to 3, 6, 9, 12, 15, 18, 21, 24 months and end of treatment will be provided. Box plots for absolute and/or relative change in platelet counts from baseline to different time points will also be provided.

6. To assess the ability of eltrombopag to **maintain platelet count $\geq 30 \times 10^9/L$** within 12 months and every 3 months until month 24

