12.8 Sample size calculation

12.8.1 Primary endpoint

Based on medical experts' advice, it is postulated that approximately 15% of patients who do not respond or relapse after a first round of steroid therapy would have sustained remission by

12 months if on steroid recycling. In this study, at least a 10% higher sustained remission rate is expected by month 12, i.e., a sustained remission rate of at least 25% by 12 months is expected in patients who will receive eltrombopag after failing first-line steroids.

The sample size calculation is based on an exact binomial test for single proportion using a target alpha level of 0.05 and power of 80% to compare the null hypothesis $H_0: P=0.15$ against the alternative hypothesis $H_1: P>0.15$, where P is proportion of patients with sustained remission by Month 12.

A sample size of 101 gives at least 80% power if the true sustained remission rate with eltrombopag is 25% or more with an actual significance level of 0.043. The null hypothesis will be rejected if the number of patients with sustained remission is 22 or more.

Table 12-1 shows the sample size, cut-off, actual alpha, beta and power for different sustained remission rates. PASS 11 (version 11.0.10) is used for the sample size calculation.

Table 12-1 Numeric results for testing $H_0: P = P_0$ versus $H_1: P > P_0$ using exact binomial test statistic

Proportion given H_0 (P_0)	Proportion given H_1 (P_1)	Sample size (N)	Cut-off (Reject H_0 if $R \geq$ This)	Actual Alpha	Actual Beta	Actual Power
0.150	0.250	101	22	0.043	0.196	0.804
0.150	0.300	48	12	0.048	0.181	0.819
0.150	0.350	28	8	0.049	0.182	0.818
0.150	0.400	22	7	0.037	0.158	0.842
0.200	0.300	116	31	0.049	0.193	0.807
0.200	0.350	56	17	0.043	0.194	0.806
0.200	0.400	35	12	0.034	0.195	0.805

At the end of the study, for decision-making purposes, the cut-off will be determined based on the final sample size and the target alpha and beta.

13 Ethical considerations and administrative procedures

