1.2 Study objectives and endpoints

Table 1-1 Objectives and endpoints

Objective(s)	Endpoint(s)
Primary Objective(s)	Endpoints for primary objective(s)
Secondary Objective(s)	Endpoints for secondary objective(s)
1. To assess ability of eltrombopag to induce sustained response off treatment by month 12 in ITP patients who relapsed or failed to respond to first-line steroid treatment.	1. Proportion of patients with sustained response off treatment by month 12 where sustained response off treatment is defined as: 
 reach platelet count $\geq 100 \times 10^9/L$ (complete response [CR]) and then maintain platelet counts around $100 \times 10^9/L$ for 2 months (no counts below $70 \times 10^9/L$) AND then taper off the drug until treatment discontinuation (see Section 9.1 of the study protocol) while, maintain platelet count $\geq 30 \times 10^9/L$ in the absence of bleeding (no bleeding AEs) or use of any rescue therapy (see Section 6.2.3 of the study protocol) until month 12.
2. To assess the duration of sustained response off treatment after treatment discontinuation by month 12 and month 24	1a. Median duration of sustained response off treatment (weeks) counted from last dose of eltrombopag to month 12 for patients with sustained response off treatment 1b. Estimated median duration of sustained response off treatment (weeks) by month 24 for patients who are in sustained response off treatment at month 12 and enter 12 months follow-up period using Kaplan-Meier method 1c. Estimated median duration of sustained response off treatment (weeks) by month 24 for all patients using Kaplan-Meier method.
3. To assess the proportion of patients maintaining a sustained response off treatment after treatment discontinuation until month 24.	2. Proportion of sustained response off treatment patients at months 15, 18, 21, and 24.
4. To assess the ability of eltrombopag to induce early response by month 1	3. Number (%) of patients with platelet count $\geq 50 \times 10^9/L$ at least once by month 1 (first month) without bleeding and no rescue therapy
5. To assess the platelet count from baseline and every 3 months until month 24	4. Number (%) of patients with at least one platelet count $\geq 30 \times 10^9/L$ after eltrombopag is re-introduced, in case of loss of response ($< 30 \times 10^9/L$ and/or bleeding event) without bleeding and no rescue therapy by month 12 and 24

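### Endpoint 1c, the all-patient median duration with 0 weeks for non-taperers, would almost certainly read 0 at the planned 25% rate; SAP 2.7.2 avoids this by an undisclosed change of population

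*Protocol*

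**What the plan says.** Protocol Table 2-1 lists endpoint 1c as "Estimated median duration of sustained remission (weeks) by month 24 for all patients using Kaplan-Meier method". SAP Table 1-1 carries it over with the new terminology: "Estimated median duration of sustained response off treatment (weeks) by month 24 for all patients using Kaplan-Meier method".

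Protocol 12.5.1, item 1c, counts duration from the last dose to relapse and adds two rules. On censoring: "The patients who do not relapse/die by month 24 will be right-censored". On patients who never come off drug, the duration is "considered as 0 for patients who do not manage to taper off eltrombopag per protocol i.e. do not reach sustained remission". The protocol does not say whether such a 0 is an event or a censored time.

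Protocol 12.8.1 gives the planning rate: "a sustained remission rate of at least 25% by 12 months is expected". This is the rate of remission held to month 12. Neither document gives a planned taper-off rate; the number able to discontinue after tapering is only a supportive summary (Protocol 12.4.4, SAP 2.5.4).

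SAP 2.7.2, item 1c, describes a different analysis. It is a Kaplan-Meier analysis of patients who achieved Step 3 (tapered off without relapse), counted from last dose to relapse, with listed events and censoring rules and no zero rule. SAP section 4 says of 2.7.2 that the analysis description was updated and that the event description and censoring rules were added. It mentions neither the new population nor the removal of the zeros.

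**The concern.** A Kaplan-Meier median is the first time at which the curve reaches 0.5 or less. If most patients enter with an event at time 0, the curve starts below 0.5 and the median is 0, however long the others stay in remission. The statistic named in both endpoint tables would then reflect the response rate and not duration, which is what secondary objective 1 asks about.

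The SAP analysis text removes the degenerate result by conditioning on having tapered off. Endpoints 1a and 1b are conditioned further, on success at month 12. A reader who takes 1c from SAP Table 1-1 as an all-patient figure would then be looking at a duration for a selected group, which overstates what a patient starting treatment can expect.

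**Working it through.** **Inputs.** N = 101 planned (Protocol 12.8.1) and 105 enrolled (SAP section 1). Null rate 0.15, planned rate 0.25 (Protocol 12.8.1). Zero rule from Protocol 12.5.1. Taper-off rate: not given, so a range is used.

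**1. The plan's own figures.** Exact binomial, reject at R or more:
- N = 101, R = 22: P(X ≥ 22 | 0.15) = 0.0433 and P(X ≥ 22 | 0.25) = 0.8042. The plan states 0.043 and 0.804.
- N = 105, R = 23: 0.0373 and 0.7995. SAP 3.1.2 states 0.037 and 0.800.

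Both are reproduced. The documents state no figure for the 1c median.

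**2. Condition for a non-zero median.** With zeros as events, S(0) = share of patients with a non-zero duration. The median exceeds 0 only if S(0) > 0.5, that is, at least 51 of 101 or 53 of 105 (50.5% in each case).

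**3. Zeros for everyone not reaching sustained remission.** With a non-zero share of 25%, P(X ≥ 53 | 105, 0.25) = 1.8e-8, and P(X ≥ 51 | 101, 0.25) = 3.3e-8. As an illustration, take 26 of 105 non-zero: S(0) = 26/105 = 0.248. The median is 0 whether those 26 relapse between weeks 30 and 78 or are all still in remission at week 78.

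**4. Zeros only for true non-taperers.** Patients who taper off and relapse before month 12 have a positive duration, so the non-zero share exceeds 25%. Two assumptions give a range:
- Constant relapse hazard, λ = −ln(share maintained)/months, from the two retrospective chronic-ITP series in Protocol 4.6. 26/49 at a median of 9 months gives 0.0704 per month; 10/12 at a median of 7 months gives 0.0260 per month.
- Last dose uniform over an assumed window. Retention to month 12 is R = the average of exp(−λu), where u is the number of months from last dose to month 12. Taper-off share = 0.25/R.

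| Last dose (months) | λ = 0.0704: R, share, P(≥ 53 of 105) | λ = 0.0260: R, share, P(≥ 53 of 105) |
|---|---|---|
| 3.2–12 | 0.745, 33.5%, 2.5e-4 | 0.894, 28.0%, 9e-7 |
| 6–12 | 0.816, 30.7%, 1.8e-5 | 0.926, 27.0%, 2.8e-7 |
| 3.2–6 | 0.595, 42.0%, 0.050 | 0.825, 30.3%, 1.2e-5 |

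The range is about 27% to 42%, and the probability of a non-zero median is at most about 0.05.

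**5. When the median would exceed 0.** With 25% in remission at month 12 and more than 50% tapered off, at least half of the taperers must have lost remission by month 12 (0.25/0.50 = 0.5). At the planned rate, then, a non-zero median needs many early relapses. A higher response rate would also produce one.

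**6. What a restricted mean would show.** Assume 30% taper off and an 18-month horizon: 0.30 × (1 − exp(−18λ))/λ months, times 30.4375/7 weeks per month. This gives about 13 weeks at λ = 0.0704 and about 19 weeks at λ = 0.0260. The median is 0 in both cases.

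**The case against.** The strongest reply is that the analysis described in SAP 2.7.2 does not have this defect: it uses Step 3 patients, assigns no zeros and lists its events and censoring. That stands. It does not deliver the endpoint that both tables name, however, and section 4 does not tell the reader that the population changed.

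A reader might infer that the median is 0 by construction. The documents do not support that. The 25% is remission held to month 12 and not a taper-off rate, and no taper-off rate is planned. The protocol is also silent on whether a 0 is an event. If the zeros were censored at time 0, those patients would leave the risk set and the median would be that of the taperers. Treating the zeros as events is the more coherent reading, because 12.5.1 keeps censoring for patients without relapse or death by month 24, and censoring the zeros would make the rule pointless. It remains a reading.

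Nor can the remission rates in Protocol Table 12-1 be entered as non-zero shares. With a non-zero share of 40% the probability is 0.019. A 40% remission rate is something else: with λ = 0.0704 and last doses over months 3.2–12 it implies 0.40/0.745 = 54% tapering off, and a probability of about 0.77. The plan expects at least 25%, so such rates are within its scope.

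The 27% to 42% range is soft. The timing windows are not in the documents, the series are retrospective and in chronic ITP, and the 26/49 counts platelets kept at 100 × 10⁹/L or more, which is not this trial's relapse definition. Using 26/49 directly as retention gives 0.25/0.531 = 47% and a probability of about 0.28.

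Finally, it would be wrong to say that no all-patient information on persistence remains. Endpoint 2 gives the proportion in remission at months 15, 18, 21 and 24 on the Full Analysis Set, and a full Kaplan-Meier curve is informative even when its median is 0.

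**Conclusion.** The point holds in a limited form. As defined in Protocol Table 2-1 and 12.5.1, with zeros counted as events, the 1c median is 0 weeks unless at least 53 of 105 patients have a non-zero duration. The probability of that at the planned rate is 1.8e-8 under the protocol's own equation of the two groups. It is at most about 0.05 under the taper-off shares of 27% to 42%, which rest on assumed hazards and timing. Step 3 patients give a usable median, but one for a selected group. The all-patient label in SAP Table 1-1 is therefore inconsistent with SAP 2.7.2, the change is not named in section 4, and apart from endpoint 2's proportions no all-patient summary of duration is left. The primary endpoint and its test are unaffected. Severity is minor to moderate, since 1c is descriptive and untested.

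**What to change.** 1. For 1c, report over the Full Analysis Set the restricted mean weeks in treatment-free remission to month 24 with a 95% CI. Patients who never taper off enter as 0, stated to be an event at time 0. Show the all-patient Kaplan-Meier curve beside it.
2. Keep the Kaplan-Meier median for Step 3 patients and label it as that group's result.
3. Align SAP Table 1-1 with SAP 2.7.2.
4. In SAP section 4, record the changed population, the dropped zero rule and the added summary, as changes made after the primary CSR was final.

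The cost is one extra descriptive summary from data already collected, plus edits to the SAP. Because the primary CSR was already final, the added summary has to be labelled post hoc. Any change to the protocol's own endpoint wording would need a written amendment under Protocol 14.1.
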